8.2 Subject Identification and Replacement of Subjects

Each subject will be assigned a unique subject identifier. This unique identifier will be on all eCRF pages.

Subjects within the initial trial subset of 18 subjects (stage 1 and 2) and in the AITL expansion cohort who do not receive at least one dose of tipifarnib will be replaced. Subjects within the initial trial subset of 18 subjects (stage 1 and 2) and in the AITL expansion cohort who are unable to provide archival tumor tissue by the end of Cycle 1 and who did not have a biopsy performed prior to initiation of tipifarnib treatment will be replaced. Replacement subjects will

have available tumor tissue identified at the time of screening. In addition, subjects with archival tissue that is of insufficient quality for biomarker evaluation, may be replaced.

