12.1 Populations

12.1.1 Efficacy Analysis

The FAS population will serve as the primary population for the analysis of tumor response and other efficacy-related data. Subjects will be excluded for FAS for the following reasons:

- No baseline data
- Failure to receive at least one dose of tipifarnib
- No post-baseline endpoint data subsequent to at least 1 dose of study drug

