12.4 Sample Size Determination

A two-stage study design was used in the initial cohort of PTCL subjects without histological or genetic selection in order to minimize the number of study subjects treated if tipifarnib were to be not efficacious. This design is intended to allow the termination of accrual in case of unacceptably low efficacy after the first subjects are evaluated in a Full Analysis Set (FAS) basis.

A two-stage design will be employed. Eleven initial study subjects will be enrolled; if 2-4 responses are observed, 7 additional subjects will be enrolled. At the completion of this cohort, treatment will be considered of further interest if the true ORR is higher than 10%. To determine the total trial size of the initial cohort of subjects, a response of interest of 30% is assumed. This design provides 80% power to detect a difference between 10% and 30% ORR at one-sided significance level of 0.087. Using this design, the probability of terminating the study at the end of stage 1 if the true ORR is 10% is 0.697 while the probability of terminating the study at the end of stage 1 if the true ORR is 30% is 0.113.

An AITL cohort will be enrolled ($N = 12$) according to Amendment 4 to the protocol. With this sample size, if 4 or more responses are observed, the probability that the true response rate in AITL subjects is at least 30% is 82.6% ([Table 6](#)).

Based on the observed antitumor activity during stage 1 and stage 2 of the study in which subjects who were found to have high levels of CXCL12 gene expression and reference CXCL12 3'UTR by retrospective analysis had better outcomes in terms of response and PFS compared to subjects with low CXCL12 expression and CXCL12 3'UTR variant sequences, a CXCL12+ cohort will be enrolled ($N = 12$) according to Amendment 6 to the protocol. With this sample size, if 2 or more responses are observed, the probability that the true response rate in CXCL12+ subjects is 10% or higher is at least 87% ([Table 7](#)).

It is assumed that the presence of CXCL12 3'UTR gene variants is of germinal, not somatic, origin. By default, CXCL12+ subjects are defined as those who present with reference CXCL12 reference gene sequence in a buccal swab assay and in whom no CXCL12 3'UTR variant or

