unknown status is observed in subsequent tumor CXCL12 gene sequencing. Subjects who were enrolled in the CXCL12+ cohort based on CXCL12+ status in the buccal swab test and later demonstrated to have a somatic tumor 3'UTR CXCL12 sequence variant will be allowed to continue treatment but may be replaced and not included in the evaluable study population for efficacy analyses.

Upon the observation of 5 confirmed responses in the AITL cohort, and 5 confirmed responses in the CXCL12+ cohort, including 2 of them in subjects with tumors of AITL histology, the trial was amended to include up to 20 additional subjects with AITL and related T follicular helper cell tumors in the AITL cohort in order to further characterize the safety and tolerability of tipifarnib in this patient population. The choice of 20 additional subjects was empirical based on the relative rarity of the patient population and no statistical hypotheses will be tested in this extension. Including Amendment 7, up to 70 evaluable subjects in total may be enrolled (dosed).

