3.2. Study Population

3.2.1. Selection of Study Population

Subjects within the initial trial subset of 18 subjects (Stage 1 and 2) and in the AITL expansion cohort who do not receive at least one dose of tipifarnib will be replaced. Subjects within the initial trial subset of 18 subjects (Stage 1 and 2) and in the AITL expansion cohort who are unable to provide archival tumor tissue by the end of Cycle 1 and who did not have a biopsy performed prior to initiation of tipifarnib treatment will be replaced. Replacement subjects will have available tumor tissue identified at the time of screening. In addition, subjects with archival tissue that is of insufficient quality for biomarker evaluation, may be replaced.

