5. ANALYSIS POPULATIONS

Full Analysis Set (FAS)

FAS will include the data on study participants who received at least one dose of tipifarnib and had at least one post-dose disease response assessment.

[REDACTED]

[REDACTED]

All Subjects as Treated (ASaT) Population

The ASaT population consists of all enrolled subjects who received at least one dose of tipifarnib and have at least one post-dose safety assessment (any laboratory, vital sign, or other safety assessment).

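### In the CXCL12+ cohort, a dosed subject may be left out of efficacy at discretion after a later tumour result; this conflicts with the full analysis set and can raise the cohort ORR

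*Protocol*

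**What the plan says.** Protocol 12.4 gives a two-part definition: "By default, CXCL12+ subjects are defined as those who present with reference CXCL12 reference gene sequence in a buccal swab assay", and in addition later tumour sequencing must show neither a 3'UTR variant nor an unknown status. It then covers subjects who pass the first part and fail the second. Those "later demonstrated to have a somatic tumor 3'UTR CXCL12 sequence variant will be allowed to continue treatment", but they "may be replaced and not included in the evaluable study population for efficacy analyses". The same section assumes that variants are of germline origin.

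The efficacy populations are defined elsewhere. Protocol 12.1.1 makes the FAS primary and lists three reasons for exclusion: no baseline data, no dose, and "No post-baseline endpoint data subsequent to at least 1 dose of study drug". SAP 5 includes participants who "received at least one dose of tipifarnib and had at least one post-dose disease response assessment". SAP 8.1 divides responders by the number of subjects in the FAS. SAP 8.2 makes ORR, PFS and DOR in a CXCL12+ subgroup part of the secondary analysis. SAP 14, which lists departures from the protocol's methods, does not mention the variant rule.

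Separate tissue rules appear in Protocol 8.2 and SAP 3.2.1. Among stage 1, stage 2 and AITL subjects with no archival tissue supplied when Cycle 1 closes, those "who did not have a biopsy performed prior to initiation of tipifarnib treatment will be replaced". Also, "subjects with archival tissue that is of insufficient quality for biomarker evaluation, may be replaced". These rules speak of replacement only.

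**The concern.** The variant rule lets someone decide, after a subject has been treated, whether that subject counts. The protocol names no decision-maker, sets no deadline, and does not require the decision to be made without sight of response. Treatment is open label (Protocol 9.7) and the investigator assesses response (Protocol 8.1). If the option were used more readily for non-responders than for responders, the cohort ORR would be biased upward. Protocol 5.3 makes that direction plausible: in the early subjects, 3'UTR variants went with progression, and all who benefited carried the reference sequence.

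The second problem is that the result is not uniquely defined. Two analysts could report different CXCL12+ ORRs from the same data, one following Protocol 12.4 and the other following the FAS. The visible SAP text does not say whether its CXCL12+ subgroup means swab-positive or tumour-confirmed.

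**Working it through.** **1. Could response be known when the decision is made?** Archival tissue may ship as late as the end of Cycle 1, which is day 28 (Protocol Table 1 footnote 6 and section 11.1). The first on-treatment scan is at Cycle 2 Day 22, which is day 28 + 22 = 50, or days 45 to 55 with the ±5-day window. A sequencing result that takes more than about 50 − 28 = 22 days (17 to 27 with the window) after late shipment would arrive after that scan. The documents give no turnaround time. Even an early result would not settle the matter, because the choice to exclude has no deadline. Knowledge of response is therefore possible, though not established.

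**2. The passages side by side.** Take a CXCL12+ cohort subject who was dosed, had a post-dose scan, and was later found to have a tumour variant.
- Protocol 12.4: may be out of the efficacy analyses.
- Protocol 12.1.1: in the FAS, since no listed exclusion applies.
- SAP 5 and 8.1: in the FAS, and so in the ORR denominator.
- SAP 14: silent.

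**3. The plan's own figure for this cohort.** With N = 12 and at least 2 responses, Protocol 12.4 gives a probability of at least 87% that the true rate is 10% or more; the Synopsis and Protocol 8.1 give 89%. A uniform prior with 2 responses in 12 gives a posterior probability of 0.866 that the rate is at least 10%. The exact binomial P(X ≤ 2 | n = 12, p = 0.10) is 0.889. The two figures thus match two methods applied to the same rule, though the documents do not name the methods.

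**4. Effect of selective replacement.** The documents give no count, so assume that k = 1 to 3 non-responders are replaced by new subjects with the same true rate p, keeping N = 12.
- With no replacement, P(at least 2 of 12 | p = 0.10) = 1 − 0.9^12 − 12 × 0.1 × 0.9^11 = 1 − 0.2824 − 0.3766 = 34.1%.
- With k replaced, failing the rule needs either no responder among the 12 and at most one among the k, or one among the 12 and none among the k. For k = 1: 0.2824 + 0.3766 × 0.9 = 0.6213, so the probability of passing is 37.9%.
- Expected ORR is p + k × p/12, apart from negligible cases where there are fewer than k non-responders to replace.

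| k | P(at least 2 of 12), true 10% | Expected ORR, true 10% | Expected ORR, true 30% |
|---|---|---|---|
| 0 | 34.1% | 10.0% | 30.0% |
| 1 | 37.9% | 10.8% | 32.5% |
| 2 | 41.5% | 11.7% | 35.0% |
| 3 | 45.1% | 12.5% | 37.5% |

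**5. Exclusion without regard to response.** If every variant carrier were removed whatever the response, the ORR would describe the tumour-confirmed group. That changes the target population; it is not selection on outcome. As an illustration, suppose 1 to 3 of 12 swab-positive subjects are variant carriers, the reference rate is 30% and the carrier rate is 0%. The swab-selected rate is then (1 − s) × 30%, with s the carrier share: 27.5%, 25.0% and 22.5%. With a carrier rate of 10% it is 28.3%, 26.7% and 25.0%. The two targets differ, so the SAP should say which one it reports.

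**The case against.** The strongest reply is that the exclusion applies a prespecified laboratory definition, since Protocol 12.4 defines CXCL12+ by swab and tumour together. Protocol 12 also defers analysis detail to the SAP, whose FAS has no variant exclusion, so an analyst who follows the SAP keeps these subjects. Both points are fair, but neither closes the gap. A definition applied under *may* is not applied uniformly, and the SAP neither withdraws the protocol's exclusion nor defines CXCL12+ in its visible text. The SAP has a redacted population that may bear on this; the redaction is not a fault, and the visible text labels the FAS as primary.

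It can also be said that little turns on the rule now. Protocol 12.4 reports 5 confirmed responses in this cohort against a benchmark of 2, the subgroup ORR is secondary, and the subjects added by Amendment 7 go to the AITL cohort, where the variant rule does not apply. This stands, and it limits the point to how the estimate is defined and reported.

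Several stronger readings are tempting but unsupported.
- A reader might infer that subjects with poor or missing tissue also drop out of efficacy. The tissue rules provide only for replacement, and both FAS definitions keep an assessed subject. The missing-tissue rule is mandatory and tied to the end of Cycle 1, before the first scheduled scan.
- A reader might take the gap between 5/15 = 33.3% of enrolled and 5/12 = 41.7% of evaluable subjects (Protocol 5.2) as the effect of this rule. The protocol does not say why three were not evaluable, so the gap cannot be attributed to it.
- A reader might conclude that any exclusion raises the ORR. Dropping one non-responder from 5/12 without replacement gives 5/11 = 45.5%, but dropping a responder gives 4/11 = 36.4%.

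**Conclusion.** The point holds for the CXCL12+ cohort and the tumour-variant rule only. The rule allows a discretionary exclusion after dosing with no safeguard against knowledge of response, and it is not reconciled with the FAS or with the SAP's ORR denominator. Under the assumed 1 to 3 selective replacements, expected ORR rises by 0.8 to 2.5 points at a true 10% and by 2.5 to 7.5 points at a true 30%. The chance of meeting the cohort benchmark at a true 10% rises by 3.8 to 11.0 points. These shifts are small beside the sampling uncertainty: the exact 95% interval for 5/12 is 15.2% to 72.3%.

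The size rests on an assumed count, on exclusions falling on non-responders, and on N staying at 12. If variants are germline, as the protocol assumes, swab and tumour should rarely disagree and few subjects would be affected. Nothing in the documents shows that the option was used, or that it was used selectively. The wording should be changed because the correction is cheap.

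**What to change.** In Protocol 12.4 and SAP 5 and 8.2, state that replacement affects accrual only, and that every subject who meets the FAS definition stays in the ORR of the cohort to which the subject was enrolled. The wording should refer to FAS subjects: saying every dosed subject would silently remove the post-baseline assessment requirement, which is a separate question.

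Define CXCL12+ in the SAP, including how unknown tumour status is classified. Report the tumour-confirmed CXCL12+ set as a sensitivity analysis, with membership set by laboratory result for all subjects regardless of response. For the tissue rules in Protocol 8.2 and SAP 3.2.1, one clarifying line is enough: replaced subjects who meet the FAS definition remain in it.

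The cost is wording, to be settled before database lock, by which time SAP 1 already requires the plan to be final. The CXCL12+ ORR may come out slightly less favourable.

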12.5 Changes in the Conduct of the Study or Planned Analyses

Only the Sponsor, upon consultation with the principal investigator may modify the protocol. The Sponsor will issue a formal protocol amendment to implement any changes. The only exception is when an Investigator considers that a subject's safety is compromised without immediate action. In these circumstances, immediate approval of the chairman of the IRB/IEC must be sought, and the Investigator should inform the Sponsor and the full IRB/IEC within 2 working days after the emergency has occurred.

The IRB/IEC must review and approve all protocol amendments. Protocol amendments that have an impact on subject risk or the study objectives, or require revision of the ICF, must receive approval from the IRB/IEC prior to their implementation.

When a protocol amendment substantially alters the study design or the potential risks or burden to subjects, the ICF will be amended and approved by the Sponsor and the IRB/IEC, and all active subjects must again provide informed consent.

13 ETHICAL AND REGULATORY ASPECTS

13.1 Responsibilities of the Investigator

The Investigator is responsible for the conduct of the trial at his/her site. He/she will ensure that the trial is performed in accordance with the clinical trial protocol and with the ethical principles that have their origin in the Declaration of Helsinki, as well as with the ICH Note for Guidance on Good Clinical Practice (ICH Topic E6, 1996) and applicable regulatory requirements. In particular, the Investigator must ensure that only subjects who have given their informed consent are included into the trial.

13.2 **Subject Information and Informed Consent**

An unconditional prerequisite for a subject's participation in the trial is his/her written informed consent. The subject's written informed consent to participate in the trial must be given before any trial-related activities are carried out.

Adequate information must therefore be given to the subject by the Investigator before informed consent is obtained (a person designated by the Investigator may give the information, if permitted by local regulations).

With the cooperation of the Sponsor, and in accordance with the Note for Guidance on Good Clinical Practice (ICH Topic E6, 1996), and the ethical principles that have their origin in the Declaration of Helsinki, the Investigator will prepare the informed consent form and other written information to be used in obtaining informed consent from the trial subjects. The investigator should cooperate with the sponsor for preparation of aforementioned written information.

Before the consent may be obtained, the potential subject (or the potential subject' legally acceptable representative) should be provided with sufficient time and opportunity to be accessed to the details of clinical trial and to decide if they would participate in the trial. All the queries related to the trial from the potential subject or legally acceptable representative should be answered by the investigator or collaborators.

In addition to providing this written information to a potential subject, the Investigator or his/her designate will inform the subject verbally of all pertinent aspects of the trial. The language used in doing so must be chosen so that the information can be fully and readily understood by lay persons.

Depending on local regulations, a person other than the Investigator may inform the subject and sign the Informed Consent Form. Where the information is provided by the Investigator, the Informed Consent Form must be signed and personally dated by the subject and the Investigator. The signed and dated declaration of informed consent will remain at the Investigator's site, and must be safely archived by the Investigator so that the forms can be retrieved at any time for monitoring, auditing and inspection purposes. A copy of the signed and dated information and Informed Consent Form should be provided to the subject prior to participation.

Whenever important new information becomes available that may be relevant to the subject's consent, the written subject information sheet and any other written information provided to subjects will be revised by the Sponsor and be submitted again to the IRB/IEC for review and favorable opinion. The agreed, revised information will be provided to each subject in the trial for signing and dating. The Investigator will explain the changes to the previous version.

13.3 Subject Identification and Privacy

A unique subject number will be assigned to each subject at inclusion, immediately after informed consent has been obtained. This number will serve as the subject's identifier in the trial as well as in the clinical trial database.

The subject's data collected in the trial will be stored under this number. Only the Investigator will be able to link the subject's trial data to the subject via an identification list kept at the site. The subject's original medical data that are reviewed at the site during source data verification by the Monitor, audits and Health Authority inspections will be kept strictly confidential.

Data protection and privacy regulations will be observed in capturing, forwarding, processing, and storing subject data. Subjects will be informed accordingly, and will be requested to give their consent on data handling procedures in accordance with national regulations.

13.4 Emergency Medical Support and Subject Card

Subjects enrolled in this clinical trial will be provided with Emergency Medical Support cards during their trial participation, which will be provided by the Sponsor or designee. The Emergency Medical Support card is based on the need to provide clinical trial subjects with a way of identifying themselves as participating in a clinical trial, and subsequently to give health care providers access to the information about this participation that may be needed to determine the course of the subject's medical treatment.

This service is designed to provide information to health care providers who are not part of the clinical trial. Clinical trial Investigators, who are already aware of the clinical trial protocol and treatment, have other means of accessing the necessary medical information for the management of emergencies occurring in their subjects.

The first point of contact for all emergencies will be the clinical trial Investigator caring for the affected subject. The Investigator agrees to provide his or her emergency contact information on the card for this purpose. If the Investigator is available when an event occurs, s/he will answer any questions. Any subsequent action will follow the standard processes established for the Investigators.

In cases where the Investigator is not available, the Sponsor or designee will provide a 24 hour contact number whereby health care providers will be given access to the appropriate Sponsor's physician or designee to assist with any information regarding tipifarnib in case of a medical emergency.

13.5 Clinical Trial Insurance and Compensation to Subjects

The Sponsor is entirely responsible for AEs that are associated with this trial and cause damage to the health of the subjects, except for AEs caused by an intentional and/or significant deviation on the part of the Investigator, the trial site, and/or the subject. Insurance coverage shall be

provided for participating to the trial. Insurance conditions shall meet good local standards, as applicable.

13.6 Institutional Review Board/Independent Ethnic Committee

Prior to commencement of the trial at a given site, the clinical trial protocol will be submitted together with its associated documents (investigator's brochure, Subject Information and Informed Consent Forms) to the responsible IRB/IEC for its favorable opinion/approval. The written favorable opinion/approval of the IRB/IEC will be filed in the Investigator Site File, and a copy will be filed in the Trial Master File at the Sponsor.

The trial must not start at a site before the Sponsor has obtained written confirmation of favorable opinion/approval from the concerned IRB/IEC. The IRB/IEC will be asked to provide documentation of the date of the meeting at which the favorable opinion/approval was given, and of the members and voting members present at the meeting. Written evidence of favorable opinion/approval that clearly identifies the trial, the clinical trial protocol version and the Subject Information and Informed Consent Form version reviewed should be provided. Where possible, copies of the meeting minutes should be obtained.

Amendments to the clinical trial will also be submitted to the concerned IRB/IEC, before implementation in case of substantial changes. Relevant safety information will be submitted to the IRB/IEC during the course of the trial in accordance with national regulations and requirements.

